## Background

Vitiligo is an acquired skin disorder characterised by depigmented patches of skin that may appear in a localised or generalised distribution. Vitiligo is estimated to affect 0.5-2% of the global population with an equal incidence between genders, age or racial/ethnic groups [1]. The exact cause of the loss of functioning melanocytes in vitiligo remains unknown but is likely to be resulted from the complex interplay of genetics, oxidative stress, and autoimmunity [2].

Although vitiligo is typically asymptomatic, it may substantially affect the psychological wellbeing of people living with the condition [3]. This could be due to the unpredictable prognosis, the current lack of cure or the perception and emotional burden associated with the visibility of vitiligo. A recent systematic review has shown that people with vitiligo are significantly more likely to suffer from depression and anxiety compared to the healthy controls [4]. However, there is a lack of knowledge of the other types of psychological symptoms/disorders that people with vitiligo experience [5].

Human society places a profound significance on appearance, aesthetics and pigmentation [6]. Vitiligo is visible on all skin types, and is particularly noticeable on dark skin tones because of the strong contrast. Given the visible difference in appearance of affected and unaffected areas of the skin the condition has been construed as being disfiguring. Some studies have suggested in those with darker skin vitiligo is correlated with a worse quality of life (QoL) [7, 8]. However, these studies have small sample sizes and psychiatric comorbidities and psychological wellbeing were not evaluated in the analyses. Further, there are other studies that indicate that people with lighter skin tones may also experience distress [9].

In addition to skin colour, the location of vitiligo lesions may also influence the overall well-being and stigmatisation experience of patients. However, inconsistent findings have been reported. A few studies showed that patients had a more significant QoL impairment when lesions were located on visible sites (e.g. face, neck and hand) [10, 11] whilst other studies did not find any relationship [12, 13]. By contrast, some studies report vitiligo lesions on more central body parts (e.g. chest, arms and trunks) are more likely to have an adverse impact on emotional wellbeing of people with the condition, perhaps because there remains anxiety as to how they might be judged by others if the condition were to be revealed [7, 14]. Indeed, the nature of reactions received from others is also likely to play an integral role in adjustment and the extent to which stigmatisation is experienced [15, 16]. Additional data from mixed method studies is needed to further understand this topic and how this may affect the possible comorbid burden of mental health conditions.

There is currently a lack of large population-based studies providing reliable estimates of the risks of psychological comorbidities associated with vitiligo in the UK. A recent observational study using the UK-THIN database [17] highlighted the burden of depression in vitiligo patients and found a bidirectional relationship between the two conditions. However, the study did not explore the associations with other forms of psychological distress and did not use a validated definition for depression. An analysis of the depression risk on the populations of different ethnicity and location of the vitiligo lesions, which can be potential sources of heterogeneity, were also not conducted.

## Objectives

To the best of our knowledge, there has only been one large population-based study assessing psychosocial comorbidities in vitiligo compared to those without the condition.[17] This study was limited only to exploring major depressive disorder (MDD, also termed recurrent depressive disorder) and used an unvalidated case definition for MDD. There have been no large-scale population studies looking at the association between vitiligo and depressive episodes (not meeting the criteria for MDD), anxiety, social phobias and other potential psychological complications of vitiligo. No current study explores the relationship with ethnicity and psychological outcomes or the associations between vitiligo location and a broader range of psychological outcomes beyond MDD. The aim of this study is therefore to fill this evidence gap.

We will conduct a large population-based study in the UK to determine the risks of comorbid mental health conditions (including depression, anxiety and other potential psychological complications of vitiligo) in people with vitiligo compared to control and to evaluate whether the relative risks may vary by different ethnicity. Reliable population-based estimates of the psychological burden associated with vitiligo are important to gain a better understanding of the condition and to ensure patients of different characteristics are provided with appropriate psychological support following diagnosis.

### Primary objectives

- Briefly describe the epidemiology of vitiligo in the dataset: vitiligo incidence of vitiligo over time and by age, sex, ethnicity and sociodemographic factors and lifetime prevalence by age and sex.
- Describe the prevalence of common mental health conditions (depressive episodes, recurrent depressive disorder and anxiety disorder), overall and stratified by sociodemographic factors and location of lesion, in adult patients diagnosed with vitiligo in a contemporary real-world population compared with matched controls without vitiligo
- Describe the incidence of common mental health conditions (depressive episodes, recurrent depressive disorder and anxiety disorders), overall and stratified by sociodemographic factors and lesion location, in adult patients diagnosed with vitiligo in a contemporary real-world population compared with matched controls in the first two years after vitiligo diagnosis.
- Describe current primary care service utilisation (primary care visits) and management patterns (secondary care referrals) in people with vitiligo with and without mental health conditions.

### Secondary objectives

- Describe the baseline prevalence and post diagnosis incidence of other potential psychological or work-related complications of vitiligo. These will comprise; time of work for illness, unemployment, social phobia, adjustment disorder, substance abuse, self-harm, overdose, and parasuicide or suicide attempts.

## Methods

### Data source

This study will use routinely collected and collated data from the Optimum Patient Care Research Database (OPCRD). This database incorporates pseudonymised primary care records from up to 700 GP practices distributed across England, Wales, Scotland and Northern Ireland. The current OPCRD cohort size is over 5 million actively registered people, and historic records available for 10.1 million people. The cohort dataset can be enhanced through direct-to-patient and direct-to-care provider questionnaires.

### Study design

The study will use the retrospectively collected data of all eligible patients within OPCRD at the date of data extraction. Within this primary care cohort, all patients with vitiligo will be identified using Read diagnostic codes. A diagnostic algorithm will be used to facilitate robust case identification vitiligo. This will comprise the identification of anyone with a vitiligo specific diagnosis code followed by exclusion of anyone with a diagnosis code for an alternative depigmenting disorder coded within a one-year period (six months before or after their first vitiligo diagnosis code). The list of alternative depigmenting disorders is shown in table 1.

Condition group	Conditions/causes included
Congenital and genetic hypomelanoses	Piebaldism Tuberous sclerosis Hypomelanosis of Ito Waardenburg syndrome Hermanski-Pudlak syndrome Griselli syndrome Menkes syndrome
Post-inflammatory hypomelanoses	Post-inflammatory leukoderma including after Atopic eczema or Psoriasis Lichen planus Pityriasis alba Lichen sclerosus
Post traumatic leukoderma	Post traumatic leukoderma
Para-malignant hypomelanoses	Cutaneous T-cell lymphoma (mycosis fungoides) Melanoma associated depigmentation
Occupational/drug induced hypomelanoses	Occupational vitiligo Other induced hypomelanoses
Para-infectious hypopigmentation	Pityriasis versicolor (or tinea versicolor) Leprosy* Leishmaniasis*
Others	Melasma Morphoea Idiopathic guttate hypomelanosis Xeroderma pigmentosum Progressive macular hypomelanosis Nevus depigmentosus Cutaneous sarcoidosis

**Table 1.** Potential differential diagnoses for vitiligo which will be used as exclusion criteria if they appear as diagnoses in the medical record within six months of the initial diagnosis of vitiligo (six months before or after the vitiligo diagnosis). \*As these conditions are extremely uncommon in the UK they will not be used in the exclusion process

The eligible vitiligo cases will comprise all incident cases of vitiligo over the last 15 years (2004-2020). Sociodemographic details will be extracted for all these cases and matched controls (described below). Sociodemographic data will comprise age group, gender, ethnicity, and socioeconomic status. Ethnicity will be categorised as follows to be consistent with the UK official census categories: White, Asian, Black African/Caribbean, Mixed, and Other. The index of multiple deprivation (IMD) will be used as a measure of socioeconomic status. This is derived from postcode at the point of data extraction and is available for nearly all patients contributing data.

Each incident case of vitiligo will be matched with an unaffected control (people without vitiligo at the date of matching) using propensity score matching (matching on the sociodemographic

variables list above and matching within primary care practice where numbers allow). The mental health conditions proposed to be examined are listed in table 2.

In addition, we will also explore whether the presence of a mental health condition at vitiligo diagnosis is related differences in service utilisation/management. We will describe the potential association between the presence of a mental health condition at vitiligo diagnosis and whether this is associated with increased primary care visits or an increased chance of a secondary care referral to dermatology. We will compare primary care visits and secondary care referral rates over the first year after diagnosis in those with a depressive illness or anxiety disorder at baseline to those without using Cox proportional hazards models adjusted for sociodemographic factors and other potential confounders. We will also report the overall primary care visit frequency and secondary care referral rate for comparison.

Condition	Description
Primary outcomes	
Depression	Recurrent depressive disorder or treated depressive episode
Anxiety	Non-phobia related anxiety episodes or disorder
Secondary outcomes	
Time off work for illness	Issue of a Med 3 certificate of fitness for work – indicating time off work for illness or other coded evidence of time off work
Unemployment	Any primary care coded evidence of unemployment
Social phobia	Diagnosis of social phobias including agoraphobia
Adjustment disorder	Diagnosis of adjustment disorder
Intentional Overdose	Any recorded intentional overdose or self-poisoning episode
Substance abuse	Record substance abuse including cannabis, alcohol, opioids, cocaine, hallucinogens, hypnotic/anxiolytic agents, or other substances.
Self-harm	Any recorded code indicative of self-harm by any method
Suicide attempt	Any recorded attempted suicide or parasuicide episode

**Table 2.** The mental health and related conditions to be explored.

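### The six-month exclusion window also governs lifelong congenital and genetic disorders, so one coded only once, more than six months before the first vitiligo code, is not excluded

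*Protocol*

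**What the plan says.** The protocol's Study design section identifies cases in two steps. Anyone with a vitiligo-specific code is selected, and the next step is "exclusion of anyone with a diagnosis code for an alternative depigmenting disorder coded within a one-year period (six months before or after" the first vitiligo code). The Table 1 caption restates the rule: the listed conditions exclude a person "if they appear as diagnoses in the medical record within six months of the initial diagnosis of vitiligo".

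The first row of Table 1 is headed "Congenital and genetic hypomelanoses" and begins "Piebaldism Tuberous sclerosis Hypomelanosis of Ito Waardenburg syndrome". Xeroderma pigmentosum and nevus depigmentosus appear in the row for other conditions.

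The only listed conditions treated differently are the two starred infections, leprosy and leishmaniasis, with the explanation "As these conditions are extremely uncommon in the UK they will not be used in the exclusion process". No condition group has a longer look-back.

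Two other statements matter here. The same section makes "all incident cases of vitiligo over the last 15 years (2004-2020") eligible, and the Primary objectives frame the mental health comparisons "in adult patients diagnosed with vitiligo in a contemporary real-world population compared with matched controls without vitiligo".

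**The concern.** A window around the vitiligo date suits a mimic that comes and goes. A pityriasis versicolor code from many years earlier says little about a pale patch seen today, so limiting the exclusion to nearby codes is sensible.

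A congenital or genetic disorder does not resolve. Whenever it was coded, it was present when the vitiligo code was entered and remains a possible explanation for the pigment loss. Under the rule as written, the same disorder excludes a person if coded five months before the vitiligo code and is ignored if its only code is five years older.

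Two outputs could be affected. Someone with lifelong pigment loss could be counted as a new vitiligo case with a wrong onset date, which would inflate vitiligo incidence. The same person would join the case arm of the mental health comparison and, if carrying no excess risk, pull the ratio towards 1.

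**Working it through.** The protocol gives no misclassification rate, code counts or sample size for this rule, so there is no stated figure to reproduce. The first step compares the passages. The others are illustrations under stated assumptions.

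**1. Side by side.**
- The text and the Table 1 caption agree: six months before or after, one year in total, for all conditions except the two starred ones.
- The first row of Table 1 is congenital or genetic by the protocol's own heading. The protocol does not describe xeroderma pigmentosum and nevus depigmentosus this way. Treating them as lifelong is a clinical judgement for the study team to confirm.
- The trigger is any code inside the window, not only the first code for the disorder. A re-coded disorder, or a vitiligo label corrected within six months, is therefore still caught.
- The mental health objectives concern adults. For an adult whose only code dates from childhood, the rule works only if the first vitiligo code fell within six months of that childhood code.

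**2. Share caught if there is one earlier code.** Assume the gap between that code and the first vitiligo code is exponential with mean *m* years. The code is caught if the gap is at most 0.5 years, so the share caught is 1 − exp(−0.5/*m*).

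| Mean gap *m* (years) | Share caught |
|---|---|
| 1 | 39% |
| 5 | 9.5% |
| 10 | 4.9% |
| 20 | 2.5% |

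Half are caught when *m* = 0.5/ln 2 = 0.72 years. With a longer mean gap, more than half are missed.

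**3. Share caught if the disorder is re-coded.** Assume codes recur at a constant rate of *r* per year. The share with at least one code in the one-year window is 1 − exp(−*r*).

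| Codes per year *r* | Share caught |
|---|---|
| 0.1 | 9.5% |
| 0.5 | 39% |
| 1 | 63% |

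Half are caught when *r* = ln 2 = 0.69 per year. The answer therefore runs from almost none caught to a clear majority caught, depending on coding habits that the protocol does not describe.

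**4. Effect on the results.** Let *f* be the share of accepted cases that are missed mimics.
- *Mental health ratio.* If mimics carry the same risk as controls, the observed ratio is about (1 − *f*) × HR + *f*. With an assumed HR of 1.50, *f* = 0.1% gives 0.999 × 1.50 + 0.001 = 1.4995, and *f* = 1% gives 0.99 × 1.50 + 0.01 = 1.495.
- *Vitiligo incidence.* The case count is inflated by 1/(1 − *f*). This is 1/0.999 = 1.001 at *f* = 0.1% and 1/0.99 = 1.010 at *f* = 1%.

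Both values of *f* are assumptions.

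**The case against.** The strongest reply has four parts.

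- *The number missed is unknown.* This stands. A reader might infer that these disorders are normally coded years earlier, so that the rule leaves most of them in the cohort or defeats the algorithm. The protocol says nothing about when or how often they are coded, and re-coding at about 0.69 per year or more would catch at least half. A reader might also spread a single code evenly over a 20- to 40-year record and conclude that only 1/40 = 2.5% to 1/20 = 5% are caught. That figure is a product of its assumption. It conflicts with the idea that the code sits in early life, and it treats the two code dates as unrelated. Where both labels come from one unsettled diagnosis, the codes would cluster, and the window would find them.
- *The effect is negligible.* This largely stands for pooled results. It might be thought larger in small ethnic subgroups or young age bands, but the protocol gives no counts to support that.
- *The protocol already treats rarity as a reason not to exclude.* This stands only in part. It dropped two infections on that ground but kept the congenital group, so it judged that group worth excluding. The starred entries also show that the table already allows condition-specific handling.
- *A wider look-back has its own cost.* This stands. Someone with a congenital disorder can also develop true vitiligo, which the Background puts at 0.5-2% of the global population. An exclusion using codes from any later date would also make eligibility depend on events long after the index date. The look-back should therefore not extend further forward than it does now.

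**Conclusion.** The point holds as a minor weakness in the case definition. The protocol chooses to exclude congenital and genetic mimics, then ignores their codes unless they fall within six months of the first vitiligo code. Nothing elsewhere in the protocol closes this gap. The mismatch does not depend on coding habits; they determine only how many people it affects.

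That number cannot be derived from the protocol. On the assumptions shown, even 1% contamination moves a ratio of 1.50 only to about 1.495 and inflates incidence by about 1%. If the missed mimics carried some excess risk of their own, up to that of true cases, the dilution would be smaller still. The text and the caption agree, so this is not a contradiction, and no stated figure is wrong. The change is desirable because it is simple, not because the main conclusions are at risk.

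**What to change.** In the Study design text and the Table 1 caption, set two rules:

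- For the congenital and genetic group, and for xeroderma pigmentosum and nevus depigmentosus if the clinical team agrees they belong with it, exclude anyone with a code at any time in the available record up to six months after the first vitiligo code.
- For the acquired conditions, keep the present six-month window on both sides.

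Report how many otherwise eligible cases the longer look-back removes. That count would show how much the rule matters. If the sponsor prefers to keep one window, reporting the number of retained cases with an earlier congenital or genetic code would serve the same purpose.

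The cost is one sentence and one changed date condition in the query. A few people with both a congenital disorder and true vitiligo would be dropped. The forward limit stays at six months, so eligibility would depend on later codes no more than it does now.

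### One matched control per vitiligo case gives away precision that existing database records could supply: near the null, 95% CIs are about 26% wider on the log scale than with four

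*Protocol*

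**What the plan says.** The control group is defined in the Protocol, Methods, Study design: "Each incident case of vitiligo will be matched with an unaffected control (people without vitiligo at the date of matching) using propensity score matching". The score uses age group, gender, ethnicity and socioeconomic status; on the last, "The index of multiple deprivation (IMD) will be used as a measure of socioeconomic status". Practice is handled by "matching within primary care practice where numbers allow".

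The singular wording sets one control per case. The plural words in brackets describe who may serve as a control, not how many. No other ratio appears in the Protocol.

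On the supply of controls, the Data source section says: "The current OPCRD cohort size is over 5 million actively registered people, and historic records available for 10.1 million people". The Background says: "Vitiligo is estimated to affect 0.5-2% of the global population". The data are retrospective, and all incident cases from 2004 to 2020 are taken.

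On use, the Objectives aim "to evaluate whether the relative risks may vary by different ethnicity". The primary objectives on prevalence and incidence of common mental health conditions call for stratified results, for incidence "overall and stratified by sociodemographic factors and lesion location". Statistical methods commits to case-control comparisons by gender and ethnicity, using odds ratios for baseline prevalence and hazard ratios for incidence. The secondary outcomes in Table 2 include self-harm, intentional overdose and suicide attempt, the last defined as "Any recorded attempted suicide or parasuicide episode".

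**The concern.** Because every eligible incident case is already included, the case count cannot be raised within this database and period. The direct design route to better precision in the case-control comparisons is more controls per case, and these already exist as records. Fixing one control per case discards that information without a stated reason.

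The loss falls where the study has least information. Ethnic variation in relative risk is a stated aim, yet minority ethnic subgroups will contain only a fraction of the cases, and a contrast between two subgroup log odds ratios carries the same dependence on the number of controls. Rare secondary outcomes have the same problem because events are few. In both settings, the ratio can decide whether a moderate association is detected.

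**Working it through.** The Protocol gives no case count, power or target precision, so there is no figure of its own to reproduce. The relative result below needs only the ratio; the absolute results need assumptions, labelled as such.

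**Supply of controls.** The Background's 0.5–2% is a global prevalence, assumed here to apply to the database. At 2%, 0.98/0.02 = 49 unaffected people per affected person; at 0.5%, 0.995/0.005 = 199.

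**Relative width.** For n cases with k controls each, control prevalence p0 and case prevalence p1:

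- Var(log OR) = 1/[n p1(1−p1)] + 1/[k n p0(1−p0)].
- At the null, with common prevalence p, this becomes (1 + 1/k)/[n p(1−p)].
- Var(log HR) is proportional to 1/HR + 1/k, which also becomes 1 + 1/k at the null.

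CI width on the log scale is proportional to the standard error. Width relative to 1:1 is sqrt[(1 + 1/k)/2]:

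| Controls per case | Width relative to 1:1 | 1:1 is wider by |
|---|---|---|
| 2 | 0.866 | 15.5% |
| 3 | 0.816 | 22.5% |
| 4 | 0.791 | 26.5% |
| 10 | 0.742 | 34.8% |

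Most of the gain is reached by four. Away from the null, in the direction the study expects, the loss is larger:

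- OR 1.5 with 10% control prevalence (assumed): 1:1 is 1.327 times as wide as 1:4.
- HR 1.5: sqrt[(1/1.5 + 1)/(1/1.5 + 0.25)] = 1.348.

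**Absolute size under assumed inputs.** The null 95% CI is exp(±1.96 SE). Power is a two-sided 5% Wald test of OR 1.5, Φ(ln 1.5/SE − 1.96), with SE taken at OR 1.5. For example, with n = 500 and p0 = 0.10, p1 = 0.143. SE is 0.196 at 1:1 and 0.148 at 1:4, so power is Φ(0.405/0.196 − 1.96) = 54% and Φ(0.405/0.148 − 1.96) = 78%.

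| Cases | Control prevalence | Null CI, 1:1 | Null CI, 1:4 | Power 1:1 | Power 1:2 | Power 1:4 |
|---|---|---|---|---|---|---|
| 10,000 | 10% | 0.91–1.10 | 0.93–1.08 | >99% | >99% | >99% |
| 5,000 | 0.5% | 0.57–1.74 | 0.64–1.55 | 35% | 46% | 56% |
| 10,000 | 0.5% | 0.68–1.48 | 0.73–1.36 | 60% | 75% | 85% |
| 20,000 | 0.5% | 0.76–1.32 | 0.80–1.25 | 88% | 96% | 99% |
| 200 (subgroup) | 10% | 0.52–1.92 | 0.60–1.68 | 26% | 34% | 41% |
| 500 (subgroup) | 10% | 0.66–1.51 | 0.72–1.39 | 54% | 69% | 78% |
| 1,000 (subgroup) | 10% | 0.75–1.34 | 0.79–1.26 | 83% | 93% | 97% |

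**Can four be found within a practice?** The Data source section gives over 5 million active people and up to 700 practices, so about 5,000,000/700 = 7,143 people per practice. Suppose an ethnic group makes up 5% of a practice (range 3–10%), split over two genders and ten equal age bands:

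- 7,143 × 0.05/20 = 17.9 people per cell (10.7 to 35.7).
- Split further by fifth of deprivation: 3.6 (2.1 to 7.1).

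Four close within-practice controls will therefore not always exist in small ethnic strata.

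**The case against.** One control per case is a valid, unbiased design, and the Protocol contradicts nothing by choosing it. The 26% would apply to any 1:1 study set against 1:4; against 1:2 it is 15.5%. No power or precision target is missed, since none is set, and the listed objectives are worded as descriptions. The case counts, outcome frequencies and OR of 1.5 all come from outside the Protocol.

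There is also a trade-off between bias and variance. By the cell sizes above, one within-practice control is often feasible where four are not. Seeking four would draw more controls from other practices or from more distant propensity scores, chiefly in the small ethnic strata the change is meant to help. Outcomes are coded primary care records, so differences in coding between practices could leave residual confounding. The full gain in the subgroup rows would then not be reached.

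Much of this stands as a limit. The gain is negligible for common outcomes in the whole cohort, nil for analyses within the vitiligo cohort, and partial where sets are incomplete; match quality is a real cost. But the objection does not remove the point. Even two controls per case raise the 500-case example from 54% to 69%, and the Protocol already allows matching outside the practice. Nor is the ratio a detail left to a later plan: the Protocol itself fixes it.

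**Conclusion.** The concern holds as an efficiency weakness that should be corrected, not as an error that invalidates the study. Near the null, 1:1 matching gives confidence intervals 26.5% wider on the log scale than 1:4; equivalently, 1:4 intervals are 20.9% narrower. That figure assumes full sets, equal follow-up and independent errors, and does not depend on case count or prevalence. What it means in practice depends on assumed case counts, prevalences and effect size. It is immaterial for common outcomes in a large cohort and material for rare secondary outcomes and for ethnic subgroups of some hundreds of cases. A subgroup of 200 remains underpowered for OR 1.5 at either ratio, and one of 1,000 is already well powered at 1:1. The propensity score includes gender, ethnicity and deprivation, so no bias is alleged.

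**What to change.** Amend the matching sentence in Study design so that each incident case is matched by propensity score to up to four people free of vitiligo at the matching date, on age group, gender, ethnicity and deprivation index. Accept fewer where four are not available, and keep the present fallback for within-practice matching. Require agreement on gender and ethnicity where feasible. This adds no precision in itself, but it keeps matched sets whole in the planned subgroups. State that the analysis will allow for the varying number of controls per case, by weights or matched-set strata.

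The cost is a revised matching rule, a larger control extract from the same database and somewhat more complex analysis; no recruitment is needed. The Protocol does not describe extraction limits or charges, so these should be confirmed. The main statistical risk is looser matching in small ethnic strata or small practices. Reporting how many controls were found per case, with covariate balance by ethnic group, would show whether the extra controls were bought at the expense of match quality.

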## Statistical methods

Standard descriptive statistics (mean, standard deviations, etc) will be used to describe the characteristics of the study cohort. The study will report the baseline prevalence (odds ratio) and incidence (hazard ratio) for each mental health condition in the vitiligo cases compared with controls. These outcomes will be compared between cases and controls in subgroups by gender and ethnicity. Within the vitiligo cohort the relationship between disease characteristics and the primary outcomes will be examined. Statistical significance for analyses will be reported using P values and 95% confidence intervals as appropriate.

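### Does excluding look-alike skin diagnoses from vitiligo cases, but not from controls, bias the case-control comparison?

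*Protocol*

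**What the plan says.** Under Methods, Study design, the Table 1 exclusion is part of finding cases: "A diagnostic algorithm will be used to facilitate robust case identification vitiligo". The algorithm takes people with a vitiligo code and then applies "exclusion of anyone with a diagnosis code for an alternative depigmenting disorder coded within a one-year period", that is, six months on either side of the first vitiligo code. The Table 1 caption uses the same anchor: the listed conditions exclude "if they appear as diagnoses in the medical record within six months of the initial diagnosis of vitiligo". One entry reads "Post-inflammatory leukoderma including after Atopic eczema or Psoriasis".

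The matching paragraph of the same section says that each incident case is "matched with an unaffected control (people without vitiligo at the date of matching"). Matching is by propensity score on age group, gender, ethnicity and deprivation, with "matching within primary care practice where numbers allow". Table 1 conditions and consultation frequency are not matching variables.

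Primary objectives sets the incidence comparison: "compared with matched controls in the first two years after vitiligo diagnosis". Statistical methods names the measures as "baseline prevalence (odds ratio) and incidence (hazard ratio) for each mental health condition in the vitiligo cases compared with controls".

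**The concern.** The two groups are built by different rules. A person with no vitiligo code has no date on which to centre the Table 1 window, so the rule as written cannot remove a control. If Table 1 conditions go with more depression or anxiety, they raise the risk among controls only and pull the odds ratio and hazard ratio down.

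The window also runs past the index date. Six of its twelve months lie after the first vitiligo code and cover the first quarter (6 of 24 months) of incidence follow-up. Whether someone counts as a case therefore depends partly on records made after follow-up has begun, which is normally a warning sign in a cohort design.

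A second worry concerns the data source. Vitiligo and every outcome are read from the same primary care record. If people who receive a vitiligo code consult more often, more of their mental illness may be recorded, which would push both ratios up. Matching on sociodemographic factors and practice balances consulting only indirectly.

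**Working it through.** The protocol gives no prevalence for Table 1 codes, no outcome rate and no sample size, so there is no stated figure to reproduce. All inputs below are assumptions.

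**1. Type of bias.** A case is removed because of a skin code, not because of death, deregistration or a mental health outcome. Nobody has to remain event-free to qualify, so there is no immortal time. What remains is a difference in the mix of skin conditions. The service-use analysis compares cases with cases, all screened alike, so the asymmetry does not reach it.

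**2. Size of the asymmetry.** Suppose vitiligo has no effect. Let q be the share of controls with an in-window Table 1 code, r their outcome risk relative to others, and p0 the risk in others. Cases have risk p0 and controls p0 × (1 − q + q × r), so

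risk ratio = 1 / (1 − q + q × r).

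| q (assumed) | r = 1.3 | r = 2.0 |
|---|---|---|
| 0.25% | 0.9993 | 0.9975 |
| 0.5% | 0.9985 | 0.9950 |
| 1% | 0.9970 | 0.9901 |
| 2% | 0.9940 | 0.9804 |
| 5% | 0.9852 | 0.9524 |

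For example, with q = 1% and r = 2.0: 1 / (0.99 + 0.02) = 1 / 1.01 = 0.9901.

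Odds ratio at q = 1%:
- p0 = 5%, r = 1.3: control risk 0.05 × 1.003 = 0.05015, odds ratio 0.9969.
- p0 = 20%, r = 2.0: control risk 0.20 × 1.01 = 0.202, odds ratio 0.25 / (0.202 / 0.798) = 0.9876.

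On the risk-ratio scale at q = 1%, a true 1.50 would be reported as 1.50 × 0.9901 = 1.485 to 1.50 × 0.9970 = 1.496.

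**3. The post-index half alone.** If codes are spread evenly over the window, half of 1% is 0.5%, giving 0.9985 to 0.9950.

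**4. Direction.** With r below 1 the sign reverses: q = 1% and r = 0.8 gives 1 / 0.998 = 1.002. The protocol does not say which applies.

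**5. Which codes count.** The rows at 2% and 5% need plain eczema or psoriasis codes to exclude a case. The Study design text limits the exclusion to alternative depigmenting disorders, and the Table 1 entry names the leukoderma that follows those two diseases. Read that way, a q of 0.25% to 1% is the more natural assumption, giving 0.9993 to 0.9901.

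**6. Using pre-index codes only.** This would keep some people whose vitiligo code was soon replaced by another diagnosis. If a share m of cases are such people with no excess risk, a true ratio R is multiplied by ((1 − m) × R + m) / R.
- m = 1%, R = 1.2: (1.188 + 0.01) / 1.2 = 0.9983.
- m = 5%, R = 1.5: (1.425 + 0.05) / 1.5 = 0.9833.

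The loss of up to 1.7% exceeds the largest post-index distortion in step 3 (0.5%).

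**7. Adjusting for consulting.** Take a true odds ratio of 1.5 and no recording bias at all. Prior-year consultations are negative binomial (mean 3 to 5, dispersion 0.3 to 1.0), depression prevalence is 5% to 20%, depression multiplies consulting by 1.5 to 2, and cases consult more because of their skin. The Mantel-Haenszel odds ratio stratified by consultation count is then:
- cases consult 10% more: 1.26 to 1.45;
- cases consult 25% more: 1.00 to 1.39.

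The adjustment can remove a real association, because existing mental illness itself raises consulting.

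**The case for a change.** The strongest case for a change is that validating the case diagnosis justifies screening cases but does not by itself justify leaving controls unscreened, since the groups should differ in vitiligo and not also in an eligibility filter. In the simple model above, giving controls the same screen returns the null ratio to exactly 1.00 at the cost of one sentence and one filter. The size is also not strictly bounded by the protocol: the post-inflammatory entry could be coded broadly, and at q = 5% and r = 2.0 the factor is 0.952. Finally, controls have no diagnosis date, so their index date is worth stating.

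The description of the asymmetry stands, and so does the arithmetic. The inference that something must change does not. The stated comparator is people without vitiligo, and someone with melasma or pityriasis versicolor properly belongs there; removing such people defines a slightly different comparator rather than correcting an error. A mirrored window would also make control eligibility depend on post-index records, extending to controls the very feature objected to in cases. The 0.952 figure needs a broad reading that the surrounding text does not favour. A shared index date is already implied, because matched controls are to be compared with cases over the two years after vitiligo diagnosis. Spelling it out is a harmless clarification that analysts would make in any event.

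On consulting, the mechanism is plausible, but nothing in the protocol shows that cases consult more. A sensitivity analysis of this kind is ordinary content for a statistical analysis plan, which is not at hand. If one is done, the incidence hazard ratio among people free of the outcome at index is a safer place for it than the baseline odds ratio.

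**Conclusion.** No change is needed. The Table 1 rule can remove only cases, partly on codes from the first six months of follow-up, but it is a legitimate check on an exposure code that controls do not have, and it contradicts nothing else in the protocol. Its likely effect on the case-control ratios is about 1% or less (risk-ratio factor 0.990 to 0.997, odds-ratio factor 0.988 to 0.997), and 0.5% or less for the post-index half. This rests on an assumed 1% of controls with an in-window code, an assumed relative outcome risk of 1.3 to 2.0 and, for the odds ratio, an assumed baseline prevalence of 5% to 20%. The direction cannot be derived from the protocol. The effect would reach about 5% only if codes for common skin diseases counted as depigmenting disorders, carried by 5% of controls at double the risk.

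The available remedies gain little or do harm. Mirroring the screen is a matter of preference that changes no result of note, the pre-index-only version can dilute the ratio more than the bias it tests, and adjusting the baseline odds ratio for consulting can turn a true 1.5 into anything from 1.00 to 1.45 when no bias is present.
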